10.4. Search Criteria for TEAE of Special Interest

The search criteria are meant to assist the process of identification of TEAE of Special Interest. However, since these criteria might not be exhaustive in some cases or may not be specific in other cases. Hence an additional blinded review of all PTs in the database may be performed by the Medical monitor, based on medical judgement, to identify any TEAE of Special Interest/TEAE Syndrome that might have been missed by the criteria or to identify any TEAE that may have been inaccurately assigned as AESI by the algorithmic search.

AESI	Search Criteria
Anaphylactic reactions	
For SMQ “anaphylactic reaction” An algorithmic approach will be used. A case must include either:
 
 1. A narrow term (a term from Category A); 2. Patient with both a term from Category B AND a term from Category C; 3. Patient with a term from Category D AND { a term from Category B - OR a term from Category C } 
For bullets 2 and 3, the search terms that are included under the SMQ for a particular event need to have the same start date (for e.g. if search shows cough (category B term) occurring at day 3 and urticaria (category C term) occurring at day 7, this event is not adjudicated as anaphylactic reaction as this is inconsistent with the clinical presentation of anaphylaxis as an acute event with simultaneous involvement of 2 or more body systems.
 
Note: manual adjudication of relevant PTs will be required by the study medical monitor, before database lock

Conjunctivitis (any type or etiology), keratitis, or blepharitis (only events that are either severe or serious or lasting ≥ 4 weeks will be reported as AESIs)	
broad CMQ conjunctivitis (Conjunctivitis, Conjunctivitis allergic, Conjunctivitis bacterial, Conjunctivitis viral, Atopic keratoconjunctivitis, Blepharitis, Dry eye, Eye irritation, Eye pruritus, Lacrimation increased, Eye discharge, Foreign body sensation in eyes, Photophobia, Ocular hyperaemia, Conjunctival hyperaemia, Xerophthalmia)
 
Blepharitis PTs (Blepharitis, blepharitis allergic)
 
AND
 
Serious AE= “Yes” OR Severity= “severe” OR lasting ≥ 4 weeks

	Note: manual adjudication of relevant PTs will be required by the study medical monitor, before database lock.
Keratitis	
Any of the following PTs:
 
 • Keratitis • Allergic keratitis • Ulcerative keratitis • Atopic keratoconjunctivitis • Herpes ophthalmic • Ophthalmic herpes simplex 
Note: manual adjudication of relevant PTs will be required by the study medical monitor, before database lock.

Severe ISRs that last longer than 24 hours	
- HLT = Injection site reactions
 
- Severity = “severe” or Serious AE =”Yes”
 
- AE duration ≥1 day

Mycosis fungoides or other forms of cutaneous T-cell lymphoma	
-HLT = Mycoses fungoides
 
-OR LLT = Sezary syndrome
 
-OR LLT = Cutaneous T-cell lymphoma
 
-OR PT = Cutaneous T-cell dyscrasia

Any severe infection	
-SOC = Infections and infestations
 
-Severity = “severe” OR Serious AE= “Yes”

Any infection requiring treatment with parenteral antibiotics	
SOC = Infections and infestations
 
- Action taken for AE = “medication”

	- ConMed: ATC3= “Antiinfectives” during the TEAE course (between start and stop dates), Route = IV, IM
Any infection requiring treatment with oral antibiotic/anti-viral/anti-fungal for longer than 2 weeks	-SOC = Infections and infestations -Action taken for AE = “medication” -Check CM: ATC3=” BETA-LACTAM ANTIBACTERIALS, PENICILLINS” OR “OTHER ANTIBACTERIALS” during the TEAE course (between start and stop dates), Route = PO and Treatment duration >14 days
Any clinical endoparasitosis	-HLT = Cestode infections -HLT = Helminthic infections NEC -HLT = Nematode infections -HLT = Trematode infections
Any opportunistic infection ^a a: The definition of opportunistic infections is referring to the recent consensus guidance for opportunistic infections in the setting of biologic therapy (K L Winthrop et al, 2015)	The following HLTs plus PTs -HLT = Pneumocystis infections -HLT* = Fungal infections NEC -HLT* = Pseudallescheria infections -HLT = Herpes viral infections -HLT = Paracoccidioides infections -HLT = Sporothrix infections -HLT = Cryptosporidia infections -HLT* = Trypanosomal infections -HLT* = Campylobacter infections -HLT* = Shigella infections -HLT* = Vibrio infections Plus the following PTs -Polyomavirus-associated nephropathy -BK virus infection -Cytomegalovirus infection -Post transplant lymphoproliferative disorder -Progressive multifocal leukoencephalopathy -*Bartonellosis -Blastomycosis -Toxoplasmosis

	
 -Coccidioidomycosis -Histoplasmosis -*Aspergillus infection -Systemic candida -Oropharyngeal candidiasis -Cryptococcosis -Listeriosis -Tuberculosis -Nocardiosis -Mycobacterial infection -*Salmonellosis -*Hepatitis B -Herpes zoster -*Strongyloidiasis -Microsporidia infection -Visceral leishmaniasis -*Hepatitis C 
Note: *Blinded manual adjudication of relevant PTs under each of HLTs listed above will be required by the study medical monitor, before database locks

Significant ALT elevation
 
ALT >3×ULN associated with total bilirubin >2×ULN; or
 
ALT >5×ULN in patients with baseline ALT ≤2×ULN; or
 
ALT >8×ULN if baseline ALT >2×ULN
	
Algorithm is to first search adverse event PT term = “Alanine aminotransferase increased” and the event must meet the following: ALT>3*ULN associated with total bilirubin>2*ULN or ALT>5*ULN with baseline ALT≤2*ULN or ALT>8*ULN if baseline ALT>2*ULN

Signature Page for VV-RIM-00114774 v1.0

ESig Approval	[Redacted] 00
---------------	---------------

ESig Approval	[Redacted] 00
---------------	---------------

ESig Approval	[Redacted] -2020 12:50:19 GMT+0000
---------------	---------------------------------------

Signature Page for VV-RIM-00114774 v1.0 Approved

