4.2.2. Secondary Endpoints

The secondary endpoints are:

Efficacy:

- Proportion of patients achieving EASI-50, EASI-75, and EASI-90 ($\geq 50\%$, $\geq 75\%$, and $\geq 90\%$ improvement from baseline) at week 16
- Absolute change in EASI scores from baseline to week 16
- Proportion of patients with both an IGA score of 0 or 1 (on a 5-point scale) and a reduction from baseline of ≥ 2 points at week 16
- Change (absolute and percent) from baseline to week 16 in weekly average of daily peak Pruritus Numerical Rating Scale (NRS)
- Proportion of patients with improvement (reduction) of weekly average of daily peak Pruritus NRS ≥ 4 from baseline to week 16
- Time to onset of effect on pruritus during the 16-week treatment period (≥ 4 -point reduction of weekly average of daily peak Pruritus NRS from baseline)
- Percent change from baseline to week 16 in SCORing Atopic Dermatitis (SCORAD)
- Change from baseline to week 16 in percent BSA of AD involvement

Safety:

- Incidence of treatment-emergent adverse events (TEAEs) from baseline through end of treatment (week 16)
- Incidence of treatment-emergent serious adverse events (SAEs) from baseline through end of treatment (week 16)
- Incidence of treatment-emergent adverse events of special interest (AESIs) from baseline through end of treatment (week 16)
- Incidence of TEAEs from baseline through end of study (week 36)
- Incidence of treatment-emergent SAEs from baseline through end of study (week 36)
- Incidence of treatment-emergent AESIs from baseline through end of study (week 36)

Pharmacokinetic:

- Concentrations of functional REGN3500 in serum by treatment regimen at each assessment timepoint from baseline to end of study (week 36)

Any exploratory endpoints will be described in the statistical analysis plan (SAP).

Note: The safety and PK endpoints will not be included in the testing hierarchy.

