10.4.4.1. Adverse Events

Definitions

For safety variables, 2 observation periods are defined:

- The pretreatment period is defined as the time from signing the ICF to before the first dose of study drug.
- The treatment-emergent period is defined as the day from first dose of study drug to the end of study. The treatment-emergent period includes the 16-week treatment period and follow-up period.
 - Treatment period: date of the first dose of study drug to week 16 visit date (study day 113 starting from the first dose of study drug if week 16 visit date is unavailable) or ET date, whichever comes first.
 - Follow-up period: date after week 16 visit date (study day 113 starting from first dose of study drug if week 16 visit date is unavailable) to EOS visit.

Treatment-emergent AEs are defined as those that are not present at baseline or represent the exacerbation of a pre-existing condition during the treatment-emergent period.

Analysis

All AEs reported in this study will be coded using the currently available version of the Medical Dictionary for Regulatory Activities (MedDRA[®]). Coding will be to lowest level terms. The verbatim text, the preferred term (PT), and the primary system organ class (SOC) will be listed.

Summaries of all TEAEs by treatment group and for overall during the treatment-emergent period, during the 16-week treatment period, and during the follow-up period will include:

- The number (n) and percentage (%) of patients with at least 1 TEAE by SOC and PT
- TEAEs by severity (according to the grading scale outlined in Section 9.5.1), presented by SOC and PT
- TEAEs by relationship to treatment (related, not related), presented by SOC and PT
- Treatment-emergent AESIs (defined with a PT or a prespecified grouping)

Deaths and other SAEs will be listed and summarized by treatment group.

Treatment-emergent AEs leading to permanent treatment discontinuation will be listed and summarized by treatment group.

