Treatment-emergent AEs (TEAEs) are AEs that developed or worsened in severity compared to the baseline during the treatment emergent period defined as the period from the administration of first study dose to the EOS visit. As only the worsening pre-existing AEs and new AEs reported during the treatment and follow-up period will be collected in the study, all AEs collected during the treatment and follow-up period are considered as TEAEs.

The skin infection TEAEs will be identified based on blinded adjudication of all reported TEAEs under the two primary system organ classes (SOCs): SOC = “Infection and infestations” or SOC = “Skin and subcutaneous tissue disorders”. Blinded adjudication will be done and finalized by the study medical monitor before database lock.

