4.6.2. Adverse Events of Special Interest

In this study, the adverse event of special interest (AESI) category includes:

- Anaphylactic reactions or acute allergic reactions that require immediate treatment
- Severe ISRs that last longer than 24 hours
- Mycosis fungoides or other forms of cutaneous T-cell lymphoma
- Any severe infection; any infection requiring treatment with parenteral antibiotics/anti-viral/anti-fungal agent; any infection requiring treatment with oral antibiotic/anti-viral/anti-fungal for longer than 2 weeks; any clinical endoparasitosis; any opportunistic infection
- Conjunctivitis (any type or etiology), keratitis, or blepharitis (only events that are either severe or serious or lasting ≥ 4 weeks will be reported as AESIs)

- Significant ALT elevation
 - a. ALT >3×ULN associated with total bilirubin >2×ULN; or
 - b. ALT >5×ULN in patients with baseline ALT ≤2×ULN; or
 - c. ALT >8×ULN if baseline ALT >2×ULN

The search criteria for AESIs are provided in Section 10.4.

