5.8.1. Adverse Events

Listing of TEAEs, serious TEAEs, and TEAEs resulting in death and study drug discontinuation will be generated.

Numbers and proportions of patients reporting TEAEs will be summarized for treatment period and follow-up period, sorted by alphabetical order of SOC and decreasing frequency of PT based on the incidence in the REGN3500 treatment group.

Summaries of TEAEs will include:

- TEAEs
 - TEAEs by SOC/PT
 - TEAEs by SOC/HLT/PT
 - TEAEs by PT
 - Common TEAEs by SOC/PT (incidence with PT $\geq 5\%$)
 - TEAEs related to study drug as assessed by the investigator by SOC/PT
 - TEAEs related to study procedure as assessed by the investigator by SOC/PT
 - TEAEs by severity by SOC/PT
 - Severe TEAEs by SOC/PT
 - Severe TEAEs related to study drug as assessed by the investigator by SOC/PT
 - Severe TEAEs related to study procedure as assessed by the investigator by SOC/PT
 - Common non-serious TEAEs by SOC/PT (incidence with PT $\geq 5\%$)
 - TEAE per 100 patient years by SOC/PT during treatment period only
- Serious TEAEs by SOC/PT
 - Serious TEAEs by SOC/PT
 - Serious TEAEs by SOC/HLT/PT
 - Serious TEAEs related to study drug as assessed by the investigator by SOC/PT
 - Serious TEAEs related to study drug as assessed by the investigator by SOC/PT
- TEAEs leading to permanent discontinuation from study treatment by SOC/PT
- Serious TEAE per 100 patient years by SOC/PT during treatment period only
- Death by SOC/PT

- Skin infection TEAEs by SOC and PT

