5.8.2. Analysis of Adverse Events of Special Interest

The adverse events of special interest (AESI) will be summarized by AESI category (see Section 10.4) and by high level term and PT.

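### The severe, parenteral and prolonged-oral infection AESI rows in SAP 10.4 search one SOC, so an adjudicated skin infection coded to the Skin SOC could be left out of AESI incidence

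*SAP*

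**What the plan says.** **Definition.** SAP 4.6.2 lists among the AESIs "Any severe infection; any infection requiring treatment with parenteral antibiotics/anti-viral/anti-fungal agent", and goes on to prolonged oral treatment, endoparasitosis and opportunistic infection. It sets no condition on the SOC to which the event is coded.

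**Skin infections.** SAP 4.6.1 states: "The skin infection TEAEs will be identified based on blinded adjudication of all reported TEAEs under the two primary system organ classes (SOCs"). The two classes it names are the infections class and "Skin and subcutaneous tissue disorders". This adjudication is mandatory, is assigned to the study medical monitor and must be final before database lock. It feeds an output listed in SAP 5.8.1 as "Skin infection TEAEs by SOC and PT".

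**AESI search.** In SAP 10.4 the rows for severe infection, for parenteral treatment and for oral treatment beyond two weeks all start from "SOC = Infections and infestations". Each then adds its own severity, seriousness or treatment condition. SAP 5.8.2 ties the output to these rows: "The adverse events of special interest (AESI) will be summarized by AESI category (see Section 10.4) and by high level term and PT".

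**Endpoint and coding.** Protocol 4.2.2 lists as a secondary safety endpoint "Incidence of treatment-emergent adverse events of special interest (AESIs) from baseline through end of treatment (week 16"), with a parallel endpoint through week 36. On coding, Protocol 10.4.4.1 says: "The verbatim text, the preferred term (PT), and the primary system organ class (SOC) will be listed". SAP 4.6.1 likewise codes each event to a preferred term and its associated primary SOC.

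**The concern.** The SAP accepts in one place that an event coded to the skin class may prove to be an infection, and it sets up a blinded process to decide. In another place it finds infection AESIs with a filter that no such event can pass, whatever the adjudicator decides and however severe the event was or however it was treated. The AESI definition in 4.6.2 gives no reason for that restriction.

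What is at stake is the completeness of the AESI count. The SAP has withdrawn all hypothesis testing, so the descriptive counts are themselves the safety result, and AESI incidence is one of the protocol's named safety endpoints. Development of REGN3500 in other diseases continues (SAP 1.1), so the safety summary keeps some use after this program ended.

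**Working it through.** The plan gives no figure to reproduce here. The check is a comparison of rules, followed by one small calculation of scale.

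**Step 1: trace one event.** Take a TEAE whose primary SOC is the skin class, which the medical monitor has adjudicated as a skin infection, and which is severe, serious, or treated with an anti-infective as the 10.4 rows specify.

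| Rule | Condition | Result |
|---|---|---|
| SAP 4.6.2, AESI definition | An infection that is severe, or treated parenterally or with prolonged oral therapy | Meets the definition if severe or so treated |
| SAP 4.6.1 and 5.8.1, skin-infection table | Adjudicated as a skin infection, from either class | Included |
| SAP 10.4, severe infection row | Infections SOC, and severe or serious | Fails on SOC |
| SAP 10.4, parenteral row | Infections SOC, and IV or IM anti-infective during the event | Fails on SOC |
| SAP 10.4, prolonged-oral row | Infections SOC, and listed oral antibacterial for more than 14 days | Fails on SOC |

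This reads the SOC in 10.4 as the primary SOC, which is the only SOC that either document says is coded.

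**Step 2: look for another way in.** The endoparasitosis and opportunistic-infection rows use high-level and preferred terms instead of an SOC filter, so they would capture the event only if its term happened to be listed. The 10.4 preface concedes that the criteria may not be exhaustive and permits a blinded review of all preferred terms to find missed AESIs, but does not require it. By contrast, the anaphylaxis, conjunctivitis/blepharitis and keratitis entries and the starred opportunistic-infection terms each say that manual adjudication is required before lock. The three infection rows carry no such note. No sentence passes the 4.6.1 result to 10.4.

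**Step 3: scale of one missed patient.** Inputs: 129 patients randomized to 5 arms (SAP 2.1 and 2.2), 1:1:1:1:1 allocation (SAP 2.3).

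- Average arm size: 129 / 5 = 25.8, about 26.
- Effect of one patient on that arm's incidence: 1 / 25.8 = 0.0388, or 3.9 percentage points.
- The AESI denominator is the safety analysis set, whose arm sizes are not given. If a treated arm had 24 patients the effect would be 1 / 24 = 4.2 points; with 28 it would be 1 / 28 = 3.6 points.

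The effect arises only for a patient with no other AESI, because incidence counts patients. The number of such patients cannot be derived: neither document gives a count of infections coded to the skin class.

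**The case against.** The strongest reply is that the SAP already provides for this. The 10.4 preface presents the search criteria as an aid, admits that they may miss events, and allows the medical monitor a blinded review to add them. The same role finalizes the skin-infection adjudication, so the person able to add the event will already have classified it. This stands as a reason to rate the point low. It does not close the gap, because the review is optional for these rows while review is compulsory for several others in the same table.

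Second, little safety information would be lost. The event would still appear in the skin-infection table, in the TEAE listings and, if severe or serious, in those TEAE summaries. Investigators must also report infection AESIs to the sponsor within 24 hours (Protocol 9.4.3). All of this is correct. However, the SAP does not say that investigator-reported AESIs enter the AESI summary when the search misses them, and the other tables do not supply AESI incidence.

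Third, a reader might infer more than the text supports:

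- That the two rules flatly contradict each other. They do not: 4.6.1 uses two classes as a pool of candidates and lets adjudication decide. The results diverge only for an event confirmed as an infection, qualifying by severity, seriousness or treatment, and not added on review.
- That such events are likely because skin infection is expected in atopic dermatitis. What matters is how often an infection carries the skin class as its primary SOC, and the documents are silent on that.
- That the skin-infection and AESI tables ought to agree. They have different scopes: the first covers all severities and treatments, the second only qualifying events.

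**Conclusion.** The point holds as a gap in the search rules. SAP 10.4 applies an SOC restriction that SAP 4.6.2 does not contain, and it makes no use of the mandatory adjudication in 4.6.1. As a result, AESI incidence could be understated if a qualifying skin-class event is adjudicated as an infection and the optional review is not done or does not add it.

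It would be wrong to conclude that AESI incidence is too low. The number of affected patients cannot be estimated from the documents and may be zero, in which case the tables do not change. If it is not zero, each missed patient with no other AESI lowers that arm's incidence by roughly 4 percentage points, on the assumptions of near-equal arms and that nearly all randomized patients were treated.

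The point is minor. The study was stopped early, the analyses are descriptive, only an abbreviated report is planned, and no efficacy conclusion depends on it. It is still worth correcting, because it makes the AESI search follow the SAP's own definition at almost no cost.

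**What to change.** In the severe, parenteral and prolonged-oral rows of SAP 10.4, widen the SOC condition to: "SOC = Infections and infestations", or TEAE adjudicated as a skin infection under Section 4.6.1. Leave the severity, seriousness and treatment conditions as they stand. This changes no AESI definition and no clinical rule.

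The cost is one phrase in three rows and a matching line of program code. The adjudication is already required, blinded and due before lock, so no new data or additional review is needed.

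An alternative is to make the blinded preferred-term review in the 10.4 preface mandatory for these three rows before database lock, as manual adjudication already is for other entries. That costs a little more medical-monitor time but needs no change to the search conditions.

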4.3. Prior / Concomitant Medication

Medications/Procedures will be recorded from the day of informed consent until the end of study (EOS) visit. Medications will be coded to the ATC level 2 (therapeutic main group) and ATC level 4 (chemical/therapeutic subgroup), according to the latest available version of WHO Drug Dictionary at the coding CRO. Patients will be counted once in all ATC categories linked to the medication.

Procedures will be coded to a Preferred Term (PT), High Level Term (HLT) and associated primary System Organ Class (SOC) according to the latest available version of MedDRA at the coding CRO.

Prior medications/procedures: medications taken or procedures performed prior to the first dose of study drug.

Concomitant medications/procedures: medications taken or procedures performed following the first dose of study drug through the EOS visit.

The prior systemic corticosteroid, immunosuppressant, phototherapy use and concomitant topical steroid eye drops or cyclosporine eye drops will be adjudicated by the clinical study director and the adjudication procedure will be documented before database lock.

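### Two adjacent infection AESI rows in SAP 10.4 use incompatible ATC3 labels, so the parenteral row may under-count, and neither row carries the full AESI definition

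*SAP*

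**What the plan says.** SAP 4.6.2, like protocol 9.4.3, defines one infection AESI as "any infection requiring treatment with parenteral antibiotics/anti-viral/anti-fungal agent". A companion AESI covers oral treatment with the same three kinds of agent for more than two weeks.

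SAP 10.4 turns these into database searches. Both rows require the infections SOC and a medication as the action taken.

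- The first row is labelled "Any infection requiring treatment with parenteral antibiotics" and adds "ATC3= “Antiinfectives” during the TEAE course (between start and stop dates), Route = IV, IM".
- The oral row is labelled for antibiotics, anti-virals and anti-fungals. It requires ATC3 to be "BETA-LACTAM ANTIBACTERIALS, PENICILLINS" or "OTHER ANTIBACTERIALS", an oral route and a duration above 14 days.

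On coding, SAP 4.3 states: "Medications will be coded to the ATC level 2 (therapeutic main group) and ATC level 4 (chemical/therapeutic subgroup". It adds: "Patients will be counted once in all ATC categories linked to the medication".

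SAP 5.8.2 tabulates AESIs by the Section 10.4 categories. The preamble to 10.4 presents the criteria as an aid that may not be exhaustive, and allows an optional blinded review of preferred terms by the medical monitor.

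**The concern.** A drug's class does not change with its route. If the oral row shows how penicillins are labelled in the ATC3 field, an intravenous penicillin does not carry the label that the parenteral row asks for. If instead the broad label is what is stored, the oral row is the one that fails. With one label per drug, the two filters cannot both work for the same drugs, and a programmer would have to guess which was meant.

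Protocol 4.2.2 makes treatment-emergent AESI incidence through week 16 and through week 36 a secondary safety endpoint. SAP 1.1 reduces the efficacy analysis to description and says that development of REGN3500 continues in other diseases, so the safety tables are the part of this study most likely to be used again. An empty row would naturally be read as no such infections, when it might only reflect a search term that matches no record.

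**Working it through.** The plan gives no figure to reproduce here. The check is a side-by-side reading followed by applying the written rule.

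**1. Where ATC levels appear in the SAP.** Section 4.3 codes medications to levels 2 and 4. Sections 5.3 and 5.4 summarise by levels 2 and 4. The rule in 6.3 for uncodable medications uses levels 2 and 4. Level 3 appears only in the two Section 10.4 rows.

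**2. The parenteral filter applied literally.** Take an infection TEAE with medication as the action taken and an intravenous drug given during the event. The row counts it only if one of the drug's ATC3 labels equals *Antiinfectives*.

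| ATC3 label(s) on the intravenous drug | Counted? |
|---|---|
| Penicillin class, as named in the oral row, alone | No |
| Other-antibacterials class, as named in the oral row, alone | No |
| Other-antibacterials class plus a second linked label *Antiinfectives* (assumed) | Yes |
| *Antiinfectives* alone (assumed) | Yes |
| Any other parenteral antibacterial, anti-viral or anti-fungal | Label not given; cannot be determined |

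The result therefore runs from no cases found to all cases found, depending on the coding. The first two lines are the only ones that use labels the SAP itself shows.

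**3. The rows against the definition.**

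| | Antibiotic | Anti-viral | Anti-fungal |
|---|---|---|---|
| AESI definition, parenteral and oral (SAP 4.6.2) | yes | yes | yes |
| Parenteral row, label | yes | no | no |
| Oral row, label | yes | yes | yes |
| Oral row, filter | two antibacterial groups | no | no |

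This mismatch stands apart from the labelling question in step 2. A long oral anti-viral or anti-fungal course meets the definition but belongs to neither group in the oral filter.

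**4. Scale, for illustration only.** SAP 2.1 gives 129 randomized patients. With 1:1:1:1:1 allocation, 129 / 5 = 25.8 per arm, and 129 × 4/5 = 103.2, or about 103 on REGN3500, assuming exact allocation and all treated. For an assumed true incidence r, the expected number of cases is 103r and the chance of at least one is 1 − (1 − r)^103:

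- r = 1%: 1.0 case; 1 − 0.99^103 = 0.645
- r = 2%: 2.1 cases; 1 − 0.98^103 = 0.875
- r = 3%: 3.1 cases; 1 − 0.97^103 = 0.957

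The documents give no incidence, so r is an assumption. These are chances that any case occurs, not that one is missed. They would equal the chance of a miss only if every case used one of the two named classes, each drug had a single label, and no review recovered the event.

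**The case against.** A reader might infer that the parenteral row must show zero in every arm whatever happens. The documents do not support that.

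- Section 4.3 allows several ATC categories per medication, so a penicillin label does not exclude a second, broader one.
- Whether *Antiinfectives* is a valid ATC3 value, and for which drugs, can be settled only from the drug dictionary.
- The SAP gives ATC3 labels for two classes only and is silent on all other parenteral anti-infectives.
- Nor does it follow that no ATC3 field exists. Section 4.3 names the levels coded and does not say that no other level is held.

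A reader might also infer that only severe or serious cases would surface elsewhere. That is too strong. SAP 5.8.1 tabulates all TEAEs by SOC and PT. It also tabulates TEAEs leading to permanent discontinuation of treatment, and protocol 7.4.2.1 makes an infection requiring a parenteral antibiotic such a reason. The opportunistic-infection row has no severity condition. Protocol 9.4.3 requires every AESI, serious or not, to be reported within 24 hours.

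All of this stands, and it limits the consequence. It does not repair the row. None of those tables identifies an infection as one treated parenterally under this AESI category. The discontinuation table cannot capture a case that arises after dosing has ended, and SAP 2.1 moved every patient still on treatment into follow-up. Neither 5.8.2 nor 10.4 says that investigators' AESI reports populate the category. The back-up review is optional and looks at preferred terms, whereas this AESI is defined by drug and route.

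It is also true that several other rows lack a manual-adjudication note: injection site reactions, mycosis fungoides, severe infection, the oral row, endoparasitosis and ALT. The omission is therefore not peculiar to this row. The note is attached to the anaphylaxis, conjunctivitis and keratitis rows and to the starred opportunistic-infection terms.

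**Conclusion.** The point holds as an inconsistency that should be reconciled before database lock. SAP 10.4 uses ATC3 at two levels of detail in adjacent rows, and the rest of the SAP works at levels 2 and 4. On a literal match with one label per drug, the parenteral row misses penicillins and other antibacterials, and so may under-count a component of a secondary safety endpoint or be empty. That conclusion rests on the single-label assumption and on the oral row showing how the field is filled. The documents cannot confirm either, and no rate of missed cases can be derived from them.

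The gap against the AESI definition needs no dictionary: the parenteral label omits anti-virals and anti-fungals, and so does the oral filter.

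The practical weight is modest. The study is descriptive, arms hold about 26 patients, and other tables would show some of the events. But with perhaps one to three cases in view under the assumed rates, missing even one could change what the row appears to say.

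**What to change.** In SAP 10.4, key both rows to an ATC level that Section 4.3 says is coded. The level 2 groups for systemic antibacterials, antimycotics and antivirals would serve. List the groups in full, so that both rows cover the three kinds of agent in the AESI definition, and correct the parenteral row's label to match. Keep the existing route and duration conditions. Add to both rows the blinded manual adjudication before database lock that the anaphylaxis, conjunctivitis and keratitis rows are assigned, with the medication record in view as well as the preferred term.

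The cost is SAP wording, one programming condition and a few more records for the medical monitor to adjudicate. No new data are needed.
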